5. PROCEDURES

5.1 Recruitment and enrollment: Potential participants will be initially identified when bringing their children to one of the five Children's Health Centers for care. On days of recruitment (which will be determined via a convenience sample based on study personnel scheduling), study personnel will access electronic health records to identify potential participants based on the age of their child. Parents of children ages 1-12 months old will be approached for study participation in a private treatment room or in the waiting room. Potential participants will be told briefly that they may qualify to participate in a 7 week study to help determine the effectiveness of a new diaper rash product called Theraworx that is currently being used as a skin protectant and for wound care. They will be told that the study will involve using Theraworx with every diaper change for 4 weeks, and also answering 8 surveys starting with a baseline, in-person survey on the day of enrollment, followed by 7 weekly, online surveys. Those who are interested in learning more about the study will be invited to a private space (if not already in one) to conduct the screening process, and if applicable, the informed consent process (Appendix A). Study eligibility will be assessed using an online screening form with stop logic

(Appendix B). For those who meet eligibility requirements, study staff will obtain written informed consent, verbally administer the baseline, in-person survey, obtain several forms of contact information, demonstrate how the Theraworx Foam should be used, and train participants in rating rash severity using a modified Diaper Dermatitis Scale (Buckley 2016) (Appendix C).

5.2 Run-in and trial periods: There will be a 3 week run-in period starting just after enrollment during which time parents will be instructed to continue their usual diapering care including use of any other diaper products/creams, and to respond to the weekly survey requests. After completing the run-in period, parents will choose to either pick up from the hospital or be sent via Fed-Ex a sufficient supply of Theraworx to last the 4 week duration of the trial period. Parents will receive written instruction on how to apply the Theraworx with every diaper change (Appendix D) and to continue to respond to the weekly survey requests.

5.3 Surveys

5.3.1 Baseline, in-person survey: Immediately following the informed consent process, study staff will verbally administer the baseline, in-person survey to participants (Appendix E). This survey will assess infant race/gender, diet (breast/bottle feeding/solid food), daily stool frequency, history of parental and sibling atopic dermatitis/childhood eczema, frequency of diaper dermatitis, creams/products used in diaper area (bath soap, emollients, diaper wipes); and who is involved in changing diapers (parent, grandparent, sibling, babysitter, daycare, etc.). It will also determine participant preference to pick up the Theraworx or have it sent to their home, and assess participant accuracy with rating visual severity of diaper rashes according to the modified Diaper Dermatitis Scale after being trained by staff. Lastly, participants will be asked to recall total number of days their infant had a diaper rash over the last 7 days, and if the number is greater than 0, to rate the rash using the modified Diaper Dermatitis Scale.

Upon completion of the baseline, in-person survey, the participant will receive an incentive debit card (ClinCard) which will be activated for the patient and charged with \$10. The participant will be instructed to keep this card for the next 7 weeks to receive future incentive disbursements for completing the online surveys.

5.3.2 Weekly, online surveys: Starting on the first Monday morning that falls at least 8 days from completion of the baseline, in-person survey and repeating each of the following Monday mornings for a total of 7 occurrences, a unique online survey link will be emailed to each participant. Each Sunday beforehand, participants will be texted and emailed a reminder to check their emails the next day and to complete the survey within 24 hours of receiving the emailed link. Each Monday morning, participants will receive a second text message reminder. By each Tuesday at noon, a list will be generated of survey non-respondents who will be contacted by phone twice that day by study staff to complete that week's survey on the phone. Each Wednesday morning, ClinCards will be charged with incentive awards for participants who complete the entire online survey. Participants who do not complete at least the first online survey will not be eligible to complete any further surveys and will be dropped from the study. This will help limit participation to those who can demonstrate capacity and willingness to complete the online survey with the intent of minimizing loss-to-follow up over the 7-week period of individual enrollment.

Weekly online surveys will assess whether the infant had any diaper dermatitis over the past 7 days, and if so, the total number of days with rash, and severity of rash on its worst day (using a modified Diaper Dermatitis Scale score (0-8)). It will also assess for any: use of other products and adjuvant therapies in the diaper area, diarrheal illnesses, new foods initiated, and changes to their contact information. The surveys during the run-in period (weeks 1-3) will confirm whether the participant prefers to pick up the Theraworx or have it sent to their home (Appendix F). During the trial period (weeks 4-6), the weekly survey will also assess how frequently Theraworx was used, and whether it was applied as a foam and/or spray (Appendix G). The final survey at the end of week 7 will be slightly longer since it will also assess satisfaction with Theraworx (in terms of its smell, feel, appearance, ease of use, whether they would recommend it to a friend, and how it compares to other diaper creams they have used) (Appendix F).

5.4 Participant reimbursement: To promote completion of online surveys and reduce risk of participant loss-to-follow up, an escalating incentive scale will be used. Completion of the baseline, in-person survey and the

first 3 weekly online surveys will be compensated with a \$10-per-survey incentive. Completion of the next 3 surveys will be compensated \$15 each. Completion of the longer, final survey will be compensated with a \$30 incentive. Thus, the maximum reimbursement for any one participant over the entire duration of participation will be \$115. All incentives will be disbursed on ClinCard debit cards.

Survey name	Baseline	Week 1 online	Week 2 online	Week 3 online	Week 4 online	Week 5 online	Week 6 online	Final
survey format	in person	online	online	online	online	online	online	online
reimbursement	\$10	\$10	\$10	\$10	\$15	\$15	\$15	\$30

5.5 Participant schedule of activities:

Procedures	T0: Screening/ Enrollment/ Baseline: Day 1	T1-1	T1: Day 8*	Т2-1	T2: Day 15*	T3-1	T3: Day 22*	T4 -1	T4: Day 29*	T5-1	T5: Day 36	T6-1	T6: Day 43*	T7-1	T7: Final Study Contact: Day 50*
Informed consent	х														
Baseline survey	х														
Survey reminder text/email/call		х	х	х	х	х	х	х	х	х	х	х	х	х	x
Weekly survey (including AE self- report)			x		x		x		x		х		x		х
Start intervention							Х								

* Actual day may be up to 8 days later to allow T1 to occur on the first Monday at least 8 days from T0.

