6.2 Potential/Reported Toxicities

- Acute Eye: Direct eye contact may cause minor irritation. If eye contact occurs, rinse thoroughly
- Acute Skin: No reports of adverse reactions to skin contact.
- Acute Inhalation: None Known
- Acute Ingestion: None Known
- Chronic Effects: None known
- Medical Conditions Aggravated by Effects: None Known

6.2.5: Product Ingredient List

- Aqua (Water)
- Cocamidopropyl Betaine
- Aloe Barbadensis Leaf Juice
- Colloidal Silver
- Tocopheryl Acetate
- Glycerin

- Allantoin
- Beta-Glucan
- Citrus Paradisi (Grapefruit) Fruit Extract
- Lauryl Glucoside
- Tetrasodium EDTA
- PEG/PPG-4/12 Dimethicone
- Methylparaben
- Propylparaben
- Parfum (Fragrance)

6.3 Agent accountability: The PI will ensure that Children's National will maintain a careful record of the inventory and disposition of Therworx using a Drug Accountability Record Form. The Children's National Clinical Research Unit Pharmacy will use this form to track lot numbers, expiration dates, and overall inventory during the study, at the end of the study and prior to destruction.

6.4 Treatment Compliance: Parents will administer Theraworx spray foam to their children. They will report use on the weekly surveys.

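### Section 5.3.2 assigns the Theraworx use items to weeks 4-6, but treatment runs through week 7; read literally, the last treated week has rash outcomes without use data

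*Combined protocol and SAP*

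**What the plan says.** Section 5.2 sets the two periods: "There will be a 3 week run-in period starting just after enrollment", and after it parents receive "a sufficient supply of Theraworx to last the 4 week duration of the trial period". Section 5.1 also tells parents to expect four weeks of use, with a baseline survey "followed by 7 weekly, online surveys". In the 5.5 schedule the intervention starts at T3 (Day 22) and the final study contact is T7 (Day 50).

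Section 5.3.2 describes three kinds of weekly survey:

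- **Weeks 1-3 (run-in).** These "will confirm whether the participant prefers to pick up the Theraworx or have it sent to their home (Appendix F").
- **Weeks 4-6.** "During the trial period (weeks 4-6), the weekly survey will also assess how frequently Theraworx was used". The same survey asks about the form of application, foam or spray, and the form cited for it is Appendix G.
- **Week 7 (final).** "The final survey at the end of week 7 will be slightly longer since it will also assess satisfaction with Theraworx". The additions listed all concern satisfaction, and the reference is again to Appendix F.

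On compliance, 6.4 says of parents: "They will report use on the weekly surveys". Section 9.3 sums rash days over a four-week post-intervention period. It also plans sensitivity analyses by reported use, and a Wilcoxon-Mann-Whitney comparison of the change in rash days between high-use and low-use groups.

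**The concern.** Section 5.3.2 ends the trial period at week 6, while 5.1, 5.2 and 5.5 end it at week 7. The conflict matters because the same sentence of 5.3.2 says which surveys carry the use and foam/spray items. A survey builder who follows it literally would leave those items off the final survey.

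The gap could not be filled from elsewhere. Parent report is the only participant-level compliance measure described: 6.3 covers pharmacy inventory, and no return or weighing of bottles is mentioned. T7 is the last contact, so no later survey could recover week-7 use.

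At stake are the analyses that depend on use. A parent who stopped before week 7 could not be told apart from one who continued, while that week's rash days would still be in the outcome. This would blur the high- versus low-use comparison and make a weak or null result harder to interpret.

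**Working it through.** **Inputs.** Run-in of 3 weeks and trial period of 4 weeks (5.2); 7 weekly surveys (5.1); intervention start on Day 22, T6 on Day 43 and T7 on Day 50 (5.5); use items named for weeks 4-6 (5.3.2). The 5.5 footnote lets actual days fall up to 8 days later; the count below uses the nominal days.

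**Step 1: reproduce the plan's treatment length.** Day 50 − Day 22 = 28 days, and 28 / 7 = 4 weeks. This agrees with 5.1 and 5.2. Also 3 + 4 = 7 weeks, which matches the seven weekly surveys. The treated weeks are therefore 4, 5, 6 and 7.

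**Step 2: count the days for which use items are named.** Weeks 4-6 run from Day 22 to Day 43: 43 − 22 = 21 days, and 21 / 28 = 75%.

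**Step 3: the remainder.** 50 − 43 = 7 days, and 7 / 28 = 25%.

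**Step 4: set exposure beside outcome.**

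| Survey | Nominal days covered | Treated | Use items named in 5.3.2 | Appendix cited | Rash days in post-intervention total (9.3) |
|---|---|---|---|---|---|
| Weeks 1-3 | Day 1 to 22 | No | No | F | No |
| Weeks 4-6 | Day 22 to 43 | Yes | Yes | G | Yes |
| Week 7 (final) | Day 43 to 50 | Yes | Not named | F | Yes |

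Week 7 is the only treated week whose rash days are counted but for which the use items are not named. The four-week post-intervention total in 9.3 can be reached only if week 7 is included.

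**Step 5: trace which analyses read the use data.** Hypotheses 1a and 1b compare the run-in with the post-intervention period (paired t-test or Wilcoxon signed rank test; McNemar's test) and use no exposure variable. The use-based sensitivity analyses and the high- versus low-use comparison do. The plan gives no rate of stopping and no cut-off between high and low use, so the number of infants who might be misgrouped cannot be calculated.

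**The case against.** A reader might infer that use is asked in weeks 4-6 alone and that week-7 exposure is certain to go unmeasured. The documents do not go that far, and the case against that reading is strong:

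- No passage restricts the items to weeks 4-6 or excludes them from week 7. The final survey is called longer because it also covers satisfaction, which reads naturally as the preceding survey with items added.
- Section 5.1 counts the final survey among the seven weekly surveys, and 6.4 has use reported on the weekly surveys without exempting a week.
- The payment table in 5.4 names the surveys Week 4, Week 5, Week 6 and Final, so the label in 5.3.2 may simply follow that naming.
- The Appendix F reference proves little. A run-in form completed before any product was used would hardly carry satisfaction items, so one citation is probably a lettering slip, or Appendix F holds more than one form.

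These points stand as reasons not to claim a certain gap. They do not remove the conflict. The text does not say which form the final survey extends, and the only form cited for it is F. Section 6.4 cannot mean every weekly survey, since weeks 1-3 precede treatment, so it depends on 5.3.2 to say which ones.

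A reader might also infer that early stoppers would be classed as full users, or that the primary result would be biased. The first has no basis, because 9.3 gives no classification rule. The second fails because 1a and 1b use no exposure data: week-7 rash days count the same whether or not use is recorded. Nor do the documents show that stopping is most likely in week 7; 5.2 plans enough product for the whole period.

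**Conclusion.** The point holds as an internal contradiction with a conditional consequence. The week range in 5.3.2 disagrees with the treatment period in 5.1, 5.2 and 5.5, and no passage assigns the use and foam/spray items to week 7. If the final survey is built as literally written, 25% of treated time has outcome without exposure, and the use-based analyses in 9.3 rest on three of four weeks. If the final survey already contains the items, what remains is a wrong week range and an ambiguous appendix letter.

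Which case applies depends on the survey forms, which are not in the documents reviewed. The 25% also assumes the nominal schedule. In either case the primary pre/post tests and the sample size are unaffected. The correction is still worth making before the surveys are built, because it is cheap and week-7 use could not be recovered afterwards.

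**What to change.** 1. In 5.3.2, change the week range for the frequency and foam/spray items from weeks 4-6 to weeks 4-7, so that it agrees with 5.1, 5.2 and 5.5.
2. State in 5.3.2 that the final survey contains these items plus the satisfaction items.
3. Correct the appendix reference for the final survey, so that it is not confused with the run-in form.
4. In 9.3, state that the high/low use grouping and the use-based sensitivity analyses are based on all four treated weeks.

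The cost is a few edited sentences and at most two more items on the final survey, which is already paid at the highest rate ($30). The sample size, visit schedule and primary analysis do not change.

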6. PHARMACEUTICAL INFORMATION

Commercially available Theraworx foam spray will be provided to participating sites by Avadim Technologies Inc.

6.1 Administration: Theraworx will be dispensed for use during the intervention period as several smaller volume bottles such that the product can be kept in several settings including the home and daycare if needed. The formulation will be dispensed in bottles with and without the foam actuator so parents can choose to apply it as a spray or foam per their own preference. During the trial period, parents will be reminded to apply Theraworx with every diaper change alone, or as a base layer if they choose to apply it with other products or creams.

6.2 Potential/Reported Toxicities

- Acute Eye: Direct eye contact may cause minor irritation. If eye contact occurs, rinse thoroughly
- Acute Skin: No reports of adverse reactions to skin contact.
- Acute Inhalation: None Known
- Acute Ingestion: None Known
- Chronic Effects: None known
- Medical Conditions Aggravated by Effects: None Known

6.2.5: Product Ingredient List

- Aqua (Water)
- Cocamidopropyl Betaine
- Aloe Barbadensis Leaf Juice
- Colloidal Silver
- Tocopheryl Acetate
- Glycerin

- Allantoin
- Beta-Glucan
- Citrus Paradisi (Grapefruit) Fruit Extract
- Lauryl Glucoside
- Tetrasodium EDTA
- PEG/PPG-4/12 Dimethicone
- Methylparaben
- Propylparaben
- Parfum (Fragrance)

6.3 Agent accountability: The PI will ensure that Children's National will maintain a careful record of the inventory and disposition of Therworx using a Drug Accountability Record Form. The Children's National Clinical Research Unit Pharmacy will use this form to track lot numbers, expiration dates, and overall inventory during the study, at the end of the study and prior to destruction.

6.4 Treatment Compliance: Parents will administer Theraworx spray foam to their children. They will report use on the weekly surveys.

7. ADVERSE DRUG REACTION REPORTING

7.1 Defining and reporting of unexpected and serious adverse events

Unexpected Adverse Events (UAEs) are defined as events that are not listed in the consent form, and are possibly related to the intervention, or are listed but occur more frequently or are more severe than anticipated. Serious Adverse Events (SAEs) are defined to include death, life threatening illness, hospitalization or prolongation of hospitalization, and persistent/significant disability. Because all intervention will occur at the participant's home unsupervised by study staff. UAEs and SAEs will be reported by the parent on the weekly online surveys. Any self-reported SAEs will be documented by study staff using the Children's National Serious Event Reporting System (SERS). Investigators will follow the Children's National guidelines for reporting SAEs. The guidelines are to report the death of a Children's National subject enrolled in an interventional study if the death is **unexpected** (not due to disease progression) and **related or possibly related to the research** within one (1) business day of learning of the event. A follow-up report must be submitted within two (2) business days. All other UAEs and SAEs will be be reported to the IRB within seven (7) business days of learning of the event. The investigator will notify the study sponsor at the same time as appropriate. Risks that are described in the protocol and consent form (expected AEs), as well as SAEs and UAEs that are unrelated to the intervention do not need to be reported to the IRB, unless the expected AE occurs more frequently or is more serious than expected. However, we will report all AEs to the DSMB, and subsequently to the IRB in the annual continuing review. Any proposed changes in the consent form or research procedures as a result of AEs will be prepared by the study team and submitted to the IRB for approval.

7.2 Stopping Criteria

7.2.1 Individual Stopping Criteria

- All protocol interventions are complete
- Failure to complete the first online survey or ≥2 post-intervention online surveys
- Death
- Lost to follow-up
- Study withdrawal
- Serious Adverse Event
- Discretion of the Study PI, such as the PI decides that continuing in the study would be harmful or no longer in the participant's best interest

7.2.2 Study stopping criteria:

- The data show a significantly increased risk of serious adverse effects during the experimental phase of the study.
- It becomes clear that successful completion of the study is not feasible (e.g. there is an excess of patient dropout, missing data, lack of recruitment, etc).

8. PATIENT CONFIDENTIALITY

To maintain patient privacy, we will be use the database product REDCap as the platform for data entry, validation and storage. The REDCap server of Children's National is located in a locked room in the Clinical Research Institute and is password protected. Access to the server is controlled by the group membership system residing on the server. In order to gain access to the data on this server, a valid user must be added. REDCap security systems require setting up a user account and password for each user to log onto the server and then he/she will be given specific permission to access the databases. This permission can only be given to data staff by the server administrator with the permission of the PI. While analyses are being conducted, data will be stored on password protected computers and backed up on the Children's National secure server which, like the REDCap server, is controlled by a group membership system requiring setting up a user account for access. Once analyses have been completed, the data will be removed from the hard drive(s) of any computer(s) used for analysis, and will be stored as de-identified electronic files on the CNHS secure server. The investigator will grant monitors and auditors from Avadim Technologies Inc. access to participant records as needed to audit the data collection process. The patient's confidentiality will be maintained and will not be made publicly available to the extent permitted by the applicable laws and regulations.

9. STATISTICAL ANALYSIS PLAN

9.1 Outcome assessment: Outcome of interest will be diaper dermatitis as assessed by parental visual assessment using a modified Diaper Dermatitis Scale Score (see Appendix C).

9.2 Sample size and power calculation: PASS 15 was used to estimate sample size needed to detect a difference of two days of perceived diaper rash between pre- and post-test scenarios using paired t-tests with non-parametric adjustment. Allowing for a large standard deviation of up to 5 days and a moderate degree of correlation between measures, a sample size of 65 with measures at both time-points would allow for detection of statistical difference at 80% power with a two-tailed p-value of 0.05. Assuming a 35% loss to follow up over the 7 weeks participation duration, we plan to recruit 100 participants. If recruitment loss exceeds 35% at the interim, we will consider raising this number to 150 participants.

9.3 Statistical Considerations

Hypothesis 1a: Parents will report fewer total days of diaper dermatitis in their infants when the infants are using Theraworx than when they are not. To evaluate Hypothesis 1a, total reported dermatitis days over the 4 week pre- and post-intervention time-points will be separately summed. For the primary analysis, only participants who completed all 8 weekly surveys will be included. Secondary analyses may consider all participants with at least two reports in each of the study periods, with missing values assumed to be the mean number of dermatitis days reported by the participant by study period. Number of dermatitis days during usual care (pre-intervention) will be compared to number of dermatitis days following use of the Theraworx Spray Foam (post-intervention) using either paired t-test or Wilcoxon signed rank test, as appropriate.

Hypothesis 1b: Parents will be less likely to report any diaper dermatitis in their infants when the infants are using Theraworx than when they are not. Occurrence of any dermatitis during the two study periods will be coded as "yes" (at least one dermatitis day) or "no" (zero dermatitis days) based on parent report of number of dermatitis days. Differences in occurrence pre- and post-intervention will be explored using McNemar's test. If numbers permit, conditional logistic regression will be considered to evaluate odds of dermatitis when using Theraworx Spray Foam compared to usual care.

Hypothesis 2a: Parents will report less use of adjuvant topical treatments (antifungals, antibacterials, steroids) for their infant's diaper dermatitis when they are using Theraworx than when they are not. Use of adjuvant topical treatments during each of the study periods will be considered as both a binary variable (any or none) as well as frequency of use, defined as number of weeks in which use was reported. Any use pre- vs. post-intervention will be evaluated using McNermar's test or conditional logistic regression. Number of uses will be compared using Wilcoxon signed rank test. Depending on numbers, marginal homogeneity tests may also be considered, treating the number of weeks as categorical variables. As use during unreported weeks will be unknown and difficult to quantify, primary analyses will consider only participants who completed all surveys.

Hypothesis 2b: Parents will report less severe diaper dermatitis based on visual assessment when their infants are using Theraworx than when they are not. Dermatitis severity will be considered in two ways: 1) average severity during each study period and 2) maximum severity during each study period. Both average and maximum severity based on the total score from the visual assessment scale will be compared pre- and post-intervention using Wilcoxon signed rank test. As in 1a, for the primary analysis, only participants who completed all 8 weekly surveys will be included. Secondary analyses may consider participants with at least two reports in each of the study periods to allow for severity averages during each study period to be calculated.

Hypothesis 3a: Parents will find Theraworx easy to apply and remove

Hypothesis 3b: Parents will find Theraworx pleasant to use (smell, feel, appearance) Descriptive statistics (median Likert scale scores and proportions) based on parent report will be used to summarize participant satisfaction with Theraworx Spray Foam.

For all analyses, a two-tailed p-value of < 0.05 will be considered significant. Sensitivity analyses based on reported Theraworx Spray Foam use, infant age, and infant sex will be considered. Difference in number of reported diaper rash days between usual care and Theraworx will be compared between high and low Theraworx use groups using Wilcoxon-Mann-Whitney test to assess whether high Theraworx usage improves number of diaper rash days better than low usage More complex longitudinal models considering weekly outcomes during usual care versus Theraworx Spray Foam using Generalized Estimating Equations may also be considered.

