4. PARTICIPANT ELIGIBILITY

4.1 Description of sites enrolling participants: Caregivers of infants ages 1-12 months old will be recruited from one of the five the Children's Health Centers (CHCs) at Children's National Health System. These health centers together treat ~30% of all children ages 0-18 years old in DC with Medicaid insurance. The population is predominantly minority (African American (85%), Hispanic (8%)) and publically insured (83%).

4.2 Inclusion criteria: Caregivers will be eligible if they can read English at the 8th grade level, and have reliable access to the internet and email for 7 weeks. English proficiency and internet access will be verified by parental completion of the first online survey within 24 hours of the request. Caregivers must also be a custodial guardian of an infant between the ages of 1-12 months old who lives with them, currently wears diapers, and has had \geq 1 diaper rash in the 2 months preceding recruitment.

4.3 Exclusion criteria: Caregivers will be excluded if their infant is immunocompromised, has a congenital disorder, or, on the day of recruitment, has a diaper rash, has a moderate to severe illness requiring hospitalization or transfer to the emergency room, or was circumcised <10 days prior. Participants who do not complete the first online survey or ≥2 post-intervention online surveys will be excluded from participating in the remainder of the study. They will also be excluded if they do not have a stable address at which they can receive a package of Theraworx at week 4 and/or are unable to pick it up at Children's National.

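### The fourth usual-care week in Section 9.3 can only be the baseline 7-day recall, which the entry rules select on, so usual care and Theraworx periods are not comparable even with no effect

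*Combined protocol and SAP*

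**What the plan says.** - Analysis (9.3, Hypothesis 1a): "total reported dermatitis days over the 4 week pre- and post-intervention time-points will be separately summed". The primary analysis is limited to participants who completed eight weekly surveys. Hypothesis 2b carries the same completeness rule.
- Analysis (9.3, Hypothesis 1b): "Occurrence of any dermatitis during the two study periods will be coded as" yes with at least one rash day and no with none. The periods are compared by McNemar's test, whose version is not specified.
- Usual care (5.2): "There will be a 3 week run-in period starting just after enrollment".
- Trial period (5.1): "using Theraworx with every diaper change for 4 weeks". Section 5.1 counts eight surveys, made up of one in-person baseline survey and seven weekly online surveys.
- Baseline recall (5.3.1): "participants will be asked to recall total number of days their infant had a diaper rash over the last 7 days".
- Entry (4.2): the infant must have had at least "1 diaper rash in the 2 months preceding recruitment".
- Exclusion (4.3): an infant who, "on the day of recruitment, has a diaper rash", is not enrolled.
- Timing (5.3.2): the first weekly survey goes out on the first Monday at least 8 days after the baseline survey and asks about the preceding 7 days.

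**The concern.** Section 9.3 does not match the schedule, and each way of resolving the mismatch creates a bias.

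If the baseline recall is counted as usual care, one of the four usual-care weeks falls inside the window used to select the infant. A single rash in that week can both admit the infant and score usual care as a yes under Hypothesis 1b, and no Theraworx week has this property. The same week also ends at a recruitment day that had to be rash-free. That removes infants with an episode in progress and lowers rash in the recall week and early run-in. The Theraworx weeks come at least three weeks later and are nearly free of either effect.

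If the recall is not counted, usual care has 21 days in which to record a rash and the trial period has 28.

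Hypotheses 1a and 1b are both under the primary objective. Using each infant as its own control does not help, because the selection acts on one period and not on the other.

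**Working it through.** **1. Counting the surveys.** Weekly surveys: 3 run-in + 4 trial = 7. Adding the baseline gives 8. Four pre-intervention weeks are therefore available only as baseline recall + T1 + T2 + T3. This matches both the 4-week sum and the eight surveys, but no section makes the assignment.

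**2. The plan's sample size (9.2), which supplies n below.** For a paired t-test, the SD of the difference is 5 × √(2(1 − ρ)). The plan calls the correlation moderate and gives no value. With ρ = 0.35 the SD is 5 × √1.30 = 5.70, and a 2-day difference at 80% power needs 66. Values of ρ of 0.40–0.45 with a non-parametric adjustment give 64–65. Then 65/(1 − 0.35) = 100. The plan's figures are reproduced, and n = 65 is used below.

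**3. The prior-rash rule alone, by hand.** Assumptions not in the documents: very short episodes arising at random at λ per 28 days, the same λ for every infant, 2 months taken as 60 days, and no treatment effect.

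- Recall week given entry: b = (1 − e^(−7λ/28)) / (1 − e^(−60λ/28))
- Usual care, any rash: 1 − (1 − b) × e^(−21λ/28)
- Theraworx, any rash: 1 − e^(−λ)

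| λ | b | Usual care | Theraworx | Difference | T1–T3 only minus Theraworx |
|---|---|---|---|---|---|
| 0.25 | 0.061/0.415 = 0.146 | 29.2% | 22.1% | +7.1 | 17.1 − 22.1 = −5.0 |
| 0.5 | 0.118/0.657 = 0.179 | 43.6% | 39.3% | +4.2 | 31.3 − 39.3 = −8.1 |
| 1 | 0.221/0.883 = 0.251 | 64.6% | 63.2% | +1.4 | 52.8 − 63.2 = −10.4 |
| 2 | 0.393/0.986 = 0.399 | 86.6% | 86.5% | +0.1 | 77.7 − 86.5 = −8.8 |

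Differences are in percentage points, taken before rounding. The enrichment is largest when rash is rare and fades as nearly every infant qualifies.

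**4. Both entry rules, by simulation with no effect.** Assumed grid of 24 scenarios: 0.25, 0.5, 1 or 2 new episodes per 28 rash-free days; mean episode 2, 4 or 7 days; no between-infant variation, or gamma variation with CV 1. The test is exact McNemar at n = 65.

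- *Prior-rash rule only:* the Hypothesis 1b difference is positive in all 24 scenarios, +0.4 to +11.4 points.
- *Both rules, no unasked days before the first survey window:* +6.2 to −4.6 points, positive in 14 of 24. Examples: 28.9% vs 22.7% (0.25 episodes of 2 days); 43.6% vs 42.3% (0.5, 4 days); 64.5% vs 64.5% (1, 2 days); 64.9% vs 69.5% (1, 7 days).
- *Both rules, 0–6 unasked days (one reading of the Monday rule in 5.3.2):* −2.0 to +7.1 points, positive in 19 of 24. Several are too close to zero for the exact count to matter. False benefit is 0.4–9.9% against 2.5% nominal.
- *Hypothesis 1a, both rules, no gap:* total days are lower in usual care in 19 of 24 scenarios, for example 4.06 vs 5.51 days (1 episode, 7 days). That is against the product.
- *Recall week left out, 3 weeks against 4:* usual care is about 5–16 points lower on any rash, against Theraworx.
- *T1–T3 against three trial weeks:* −7.7 to +0.1 points, with false benefit at or below 1.6%.

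**The case against.** A reader might infer that the plan as written makes Hypothesis 1b favour Theraworx with no effect. The documents do not support that, for four reasons.

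- **Direction.** The recruitment-day exclusion in 4.3 pushes the other way. The net sign depends on how often rash occurs, how long it lasts, and how many days pass before the first survey window. The documents give no rash rate or episode length for this population.
- **Size.** The largest excess arises at 0.25 episodes per month, where mean usual-care rash is only about 0.9–1.6 days over four weeks. The 2-day reduction used for sample size would then be impossible. At one episode per month, where that reduction is readily achievable (about 2.5–3.9 days), the excess is about 0.9–2.3 points in scenarios with a 5-day gap.
- **Test version.** With the uncorrected McNemar test, false benefit at 0.25 episodes is 10–15%. In the same scenarios the exact test gives about 6–9%. The plan does not say which will be used.
- **Assignment.** Sections 5.1, 5.2 and 5.3.2 describe a 3-week run-in and keep the baseline survey apart from the seven weekly ones. The wording in 9.3 may be a drafting slip.

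All four stand, and they limit the point to a bias of uncertain direction. They do not remove it. If 9.3 is a slip, the comparison becomes 3 weeks against 4, which is also biased. The weekly-outcome GEE models in 9.3 would put the weeks on an equal footing, but they are only optional.

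**Conclusion.** The mismatch between 9.3 and the schedule follows from the documents. That the baseline recall fills the gap is an inference, though it is the only week available. If it is used, two opposing selection rules act on usual care, and the two periods are not comparable under no effect.

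For Hypothesis 1b the bias can favour Theraworx by up to about 7 points, with exact-test false benefit up to about 10% against 2.5% nominal at n = 65, when episodes are infrequent or short. It is near zero or reversed when they are frequent or long. Hypothesis 1a mostly runs against the product. If the recall is not used, any rash is biased about 5–16 points against Theraworx.

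These sizes rest on assumed rash rates, episode lengths and survey gaps, and they ignore age trend, season and recall error. The change of sign across the range is more reliable than any single figure. The change should be made before analysis, because neither reading of 9.3 gives a fair comparison.

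**What to change.** In Section 9.3:

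1. State that the baseline 7-day recall is not an outcome week, and keep it as a baseline descriptor or covariate.
2. Hypothesis 1a: compare rash days per reported week in T1–T3 with rash days per reported week in the trial period.
3. Hypothesis 1b: compare any rash in T1–T3 with any rash in three trial weeks fixed in advance, or analyse the weekly yes/no reports. Name the version of McNemar's test.
4. Replace the 4-week and eight-weekly-survey wording to match, including under Hypothesis 2b.
5. State as a limitation that the rash-free recruitment-day rule still depletes early run-in. This biases modestly against the product, by about 0 to 8 points on any rash depending on episode length and the gap before the first survey window.

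The cost is SAP wording only, with no new data. Usual care then rests on 21 rather than 28 days, so precision is slightly lower, and Hypothesis 1a must be reported per week.
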